4. DRUG-SPECIFIC ANALYSES

This appendix describes the analyses and parameters that apply only to the comparison between the solanezumab arm and the relevant control group. Such analyses will be performed in addition to analyses described in the main SAP.

4.1 Secondary Efficacy Endpoints

- Clinical
 - Clinical Dementia Rating™ (CDR), including Clinical Dementia Rating Sum of Boxes™ (CDR-SB) and clinician's diagnostic assessment
 - Geriatric Depression Scale (GDS)
 - Neuropsychiatric Inventory Questionnaire (NPI-Q)
 - Functional Assessment Scale (FAS)
 - Mini-Mental State Examination (MMSE)

- Cognitive
 - International Shopping List Test (12-Item Word List Learning): 3 learning trials, Immediate Recall, 30-min Delayed Recall (Cogstate)
 - Groton Maze Learning Test: Timed Chase Task, 5 learning Trials, Immediate Recall, 30-min Delayed/Reversed Recall (Cogstate)
 - Trailmaking Test parts A & B
 - WMS-R Digit Span
 - WAIS-R Digit-Symbol Substitution Test
 - Raven's Progressive Matrices (Set A)
 - Category Fluency (Animals & Vegetables)
 - WMS-R Logical Memory (Immediate & Delayed Recall)
 - Newly Proposed Composite: (1) Digit Span backwards; (2) Logical Memory (Immediate); (3) Trailmaking B; (4) Category Fluency (Animals)

- Imaging
 - Brain amyloid load as measured by [¹¹C]PiB-PET
 - Brain amyloid load as measured by florbetapir PET

- Brain glucose metabolism as measured by fluorodeoxyglucose (FDG)-PET
- Brain atrophy as measured by cortical thickness of regions of interest, whole brain volume and ventricular volume (volumetric MRI)
- Brain tau load as measured by Tau PET
- CSF
 - A β 40 and 42, free and total
 - Tau and pTau
 - Neurofilament light chain (NfL)
- Plasma
 - NfL
 - A β 40 and 42, total
 - Anti-drug antibodies (ADA)

4.2 Exploratory Endpoints

- Cognitive
 - Cogstate Detection Task
 - Cogstate Identification Task
 - Cogstate One Card Learning Test
 - Cogstate One-Back Task
 - Behavioral Pattern Separation Object Task
 - Memory Complaint Questionnaire (MAC-Q)
- Plasma
 - Tau, pTau

Each of these endpoints will be analyzed using MMRM as specified in [Section 12.1.6.9](#), LME as specified in [Section 12.1.6.8](#), and LME with dose adjustment as specified in [Section 12.1.7](#) of the main SAP.

4.3 Drug-specific Safety Endpoints

4.3.1. Infusion Reaction Adverse Events

Infusion reaction AEs will be summarized, by treatment group, as the number of subjects with reported events that map to any one of the following:

- High-level term (HLT) of infusion site reaction
- HLT of administration site reaction
- HLT of injection site reaction

Analyses to be conducted based on an integrated search using all terms from all of the above categories (3 HLTs) combined:

- A summary rolling up of all terms within each of the above categories separately.
- Within each of the above categories, the associated PTs that were reported will be summarized.

The PTs will be listed for summary within each category in decreasing order of incidence for solanezumab-treated subjects.

4.3.2. Hypersensitivity (Immediate and Non-Immediate)

Analyses will be performed for 2 main time periods to support an assessment of potential immediate hypersensitivity, including anaphylaxis and infusion-related reactions (IRRs), as well as potential non-immediate hypersensitivity.

Time Period A, of potential immediate hypersensitivity, includes all TEAEs occurring on the day of study drug administration.

Time Period B, of potential non-immediate hypersensitivity, includes all TEAEs occurring strictly after the day of study drug administration (but prior to subsequent drug administration).

Analyses for both time periods are based on the following:

- Anaphylactic reaction SMQ (20000021; narrow, algorithm per MSSO SMQ guide, and broad)

- Hypersensitivity SMQ (20000214; narrow and broad)
- Angioedema SMQ (20000024; narrow and broad)

The number and percentage of subjects who experienced a TEAE for the following will be analyzed for each of the two time periods:

- All narrow and algorithmic terms from the 3 SMQs indicated above, combined
- All narrow and broad scope terms within each SMQ, separately
- For each narrow, algorithmic, and broad query, the associated PTs that were reported will be summarized.

For Time Period A only, the number and percentage of each PT that is not in any of the 3 SMQs will be summarized overall and by individual PT.

The PT and LLT will be listed as a summary in decreasing order of incidence for solanezumab-treated patients. Note that an individual patient may contribute multiple events. Also, a single event may satisfy multiple SMQs, in which case the event contributes to every applicable SMQ.

4.3.3. Analyses of Immunogenicity Data

Immunogenicity Definitions

Figure 3 provides an overview of the immunogenicity assay process. At a high level, an individual sample is potentially examined multiple times, in a hierarchical procedure, to produce a sample solanezumab ADA assay result and potentially a sample solanezumab neutralizing antibody (NAb) assay result. The drug tolerance of each assay, the possible values of titers, and the cutpoints applied are operating characteristics of the assays and the hierarchical testing procedure of Figure 3.

It can be the case that the presence of high concentrations of solanezumab will affect the measurements of the presence of ADA or NAb, and conversely high levels of ADA or NAb may affect the measurement of LY concentration. Thus an LY drug concentration, assessed from a sample drawn at the same time as the ADA sample, plays a key role in clinical interpretation of a sample when the laboratory result is Not Detected, as shown in Figure 3.

The rest of this section defines the component concepts of Figure 3 in greater detail.

[figure not shown]

Figure 3: Flow Chart of ADA Assessment with Clinical Interpretation of the Various Result Possibilities

Definitions of Sample ADA Status (Tables 20 and 21)**Table 20: Sample ADA Assay Results**

Sample Laboratory Result	Explanation
Detected	ADA are detected and confirmed.
Not Detected	The raw result as reported from the laboratory indicates ADA not detected. The clinical interpretation of such results depends on other factors (see below).
NO TEST, QNS (quantity not sufficient), etc.	Sample exists but was un-evaluative by the assay

Table 21: Sample Clinical ADA Interpretation Results

Sample Clinical Interpretation	Explanation
ADA Present	ADA assay result is Detected
ADA Not Present	ADA assay result is Not Detected and simultaneous drug concentration is at a level that has been demonstrated to not interfere in the ADA detection method (i.e., drug concentration is below the assay's drug tolerance level). If drug concentration is not available for a treatment-period sample, the sample is inconclusive (see below). For pre-treatment samples and patients receiving placebo, drug concentration is not assessed and is assumed to be below the assay's drug tolerance level.
ADA Not Detected, Drug Concentration Not Available	If drug concentration is expected per protocol but not available, the immunogenicity sample is "ADA Not Detected, Drug Concentration Not Available" for the purpose of patient listings. For the purpose of TE ADA computation (see below), these samples are taken to be ADA Not Present.
ADA Inconclusive	ADA assay result is Not Detected but drug concentration in the sample is at a level that can cause interference in the ADA detection method, or drug concentration is planned per protocol but is not available.
ADA Missing	ADA sample not drawn, QNS, not tested, etc., causing there to be no laboratory result reported or the result is reported as "no test".

Parallel terminology applies for Neutralizing ADA (NAb) Detected, NAb Not Detected, NAb Present, NAb Not Present, NAb Inconclusive, NAb Missing. Anti-drug antibodies and Neutralizing ADA (NAb) are distinct assays and have different assay operating characteristics.

A post-baseline immunogenicity sample with ADA Present is said to have TE ADA titer if the titer meets the criteria to classify the subject as TE ADA+.

Definitions of Immunogenicity Assessment Periods

Immunogenicity Baseline Observations: Baseline period for immunogenicity assessment for each subject includes all observations on or prior to the date of the first administration of study drug. In instances where multiple baseline observations are collected, to determine subject ADA status the lowest titer/not detected is used to determine treatment-emergent status (see below).

Immunogenicity Post-baseline Period Observations: Post-baseline period observations for each subject includes all observations after the first administration of study drug.

Definitions of Subject ADA Status

Subject evaluable for treatment-emergent ADA: A subject is evaluable for TE ADA if the subject has a non-missing baseline ADA result, and at least one non-missing post-baseline ADA result.

Treatment-emergent ADA positive (TE ADA+) subject: A subject who is evaluable for TE ADA is treatment-emergent ADA positive (TE ADA+) if either of the following holds:

- a. The subject has baseline status of ADA Not Present and at least one post-baseline status of ADA Present with titer $\geq 2 \times$ MRD, where the MRD is the minimum required dilution of the ADA assay.
- b. The subject has baseline and post-baseline status of ADA Present, with the post-baseline titer being 2 dilutions (4-fold) greater than the baseline titer. That is, the subject has baseline status of ADA Present, with titer 1:B, and at least one post-baseline status of ADA Present, with titer 1:P, with P/B ≥ 4 .

Treatment-emergent ADA Inconclusive subject: A subject who is evaluable for TE ADA is TE ADA Inconclusive if $\geq 20\%$ of the subject's post-baseline samples, drawn pre-dose, are ADA Inconclusive and all remaining post-baseline samples are ADA Not Present.

Treatment-emergent ADA negative (TE ADA-) subject: A subject who is evaluable for TE ADA is TE ADA negative (TE ADA-) when the subject is not TE ADA+ and the subject is not TE-ADA Inconclusive.

Immunogenicity Statistical Analyses

A listing will be provided of all immunogenicity assessments for those patients who at any time had ADA Present. This includes the laboratory ADA assay result (Detected or Not Detected), solanezumab concentration from a simultaneous pharmacokinetic sample, and the clinical interpretation result that combines these (ADA Present, ADA Not Present, ADA Inconclusive, Missing). When Detected, a titer will be included, and TE ADA+ observations will be flagged. Also included, when the NAb assay was performed, will be the laboratory NAb assay result (Detected or Not Detected) and the NAb clinical interpretation result (NAb Present, NAb Not Present, NAb Inconclusive, Missing).

For the remainder of this section, mention of ADA result and NAb result will refer to the respective clinical interpretation result.

The number and proportion of patients who are TE ADA+ will be tabulated by treatment group, where proportions are relative to the number of patients who are TE ADA evaluable, as defined above. This analysis will include all post-baseline observations and will examine solanezumab ADA and solanezumab NAb. The tabulation will include the number and proportion of patients with ADA Present at baseline, and also the number and proportion of TE ADA+ patients exhibiting NAb+. For analysis sets involving both solanezumab and placebo, results between solanezumab- and placebo-treated groups will be compared using a Cochran-Mantel-Haenszel test stratified by study, for TE ADA+ and for TE ADA+ with NAb+.

A summary will be provided of the number and percentage of solanezumab-treated patients experiencing TEAE (overall and by PT) by patient TE ADA status (TE ADA+, TE ADA-, TE ADA Inconclusive). The PT will be ordered by decreasing incidence in TE ADA+ status group.

In order to assess the clinical relevance of TE immunogenicity, specific acute and non-acute AEs will be evaluated. A listing will be provided of these events for all patients who were TE ADA+. This listing includes a time course of ADA (clinical interpretation result, plus flags for samples with TE ADA titer or NAb+ samples) along with the AE. Listings with the same structure will be provided of (i) these events of interest for patients who had ADA Present at any time (including baseline) but who were not TE ADA+, and (ii) all TEAE for TE-ADA+ patients.

The time from first dose to the first TE ADA titer will be summarized cumulatively for representative time intervals over the course of the study.

Sample clinical interpretation result, represented as ADA Not Present, ADA Inconclusive, or as a titer value for ADA Present samples, will be displayed in a shift table from baseline to maximum post-baseline. For patients with a post-baseline ADA Present sample, the maximum post-baseline value is the maximum titer observed at any time post-baseline. For patients without a post-baseline ADA Present sample, the maximum value is ADA Inconclusive, if such a result was observed. If no patients had maximum value of ADA Inconclusive, then ADA Inconclusive will not be displayed in the table.

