13.2 Adverse Events

An AE is defined as any untoward medical occurrence in a clinical trial subject, whether it is considered to be drug related. AEs will be recorded and assessed as to whether they are treatment-emergent adverse events (TEAEs). TEAEs are defined as events that first occur or worsen (increase in severity) after the first dose of the study drug. The onset date/time of an AE will be compared to the date/time of first dose of the study drug to determine if the AE is treatment emergent or not. If the AE onset date is missing or partial, the date will be compared as far as possible with the date of first dose of the study drug. AEs will be assumed to be treatment-emergent unless there is clear evidence (through comparison of partial dates and/or collected assessment of

whether the AE started prior to the first dose of the study drug) suggesting the AE started prior to the first dose of study medication.

An overall summary of TEAEs will be presented with the number and percentage of subjects having a TEAE, a severe TEAE, a TEAE related to study treatment, a serious TEAE, a TEAE leading to study discontinuation, and a TEAE with an outcome of death. The overall summary will be presented for each study drug arm, the mutation positive placebo arm, and the mutation negative placebo arm. The summary will also be reported by doses (low (the initial dose) vs high (escalated doses) at the time of initiation of the high dose). The number of TEAEs per patient-year of exposure will also be presented, where patient years will be the sum of treatment duration in a column converted to years.

All TEAEs will be summarized by the *Medical Dictionary for Regulatory Activities* (MedDRA) System Organ Class (SOC) and Preferred Term (PT). The dictionary version will be established and documented during the blinded data review meeting prior to lock of the data.

Subjects experiencing more than one TEAE by SOC and PT will only be counted once at the preferred terminology level in AE frequency tables, but each unique TEAE will be included in the total number of TEAEs (where provided) for each SOC and PT. The overall summary for SOC and PT will be presented for each study drug arm, the mutation positive placebo arm, and the mutation negative placebo arm. The summary will also be reported by doses (low (the initial dose) vs high (escalated doses) at the time of initiation of the high dose).

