The variance-covariance matrix, Σ , is assumed to (estimated from the DIAN-OBS data) have standard deviations of 0.329, 3.431, 0.280, 0.290 for MEMUNITS, MMSE, WAIS, ISLT, respectively. The pairwise correlations are 0.091 (MEMUNITS and MMSE), 0.136 (MEMUNITS and WAIS), 0.089 (MEMUNITS and ISLT), 0.419 (MMSE and WAIS), -0.088 (MMSE and ISLT), and -0.070 (WAIS and ISLT).

The mean function for each component is

$$f(x) = \begin{cases} 0 & x \leq -15 \\ (1 + [x] - x)\alpha_{[x]} + (x - [x])\alpha_{[x]+1} & -15 < x \leq 15. \\ \alpha_{15} & x > 15 \end{cases}$$

The assumed mean changes as a function of the EYO values for the observational data are presented in Table 13.

Table 13: The Mean for Each Endpoint

α_{EYO}	MEMUNITS	MMSE	WAIS	ISLT
α_{-15}	0	0	0	0
α_{-14}	-0.111	-0.118	-0.093	-0.116
α_{-13}	-0.224	-0.238	-0.192	-0.235
α_{-12}	-0.341	-0.360	-0.297	-0.351
α_{-11}	-0.462	-0.481	-0.404	-0.457
α_{-10}	-0.585	-0.605	-0.513	-0.555
α_{-9}	-0.706	-0.730	-0.622	-0.647
α_{-8}	-0.824	-0.860	-0.736	-0.738
α_{-7}	-0.941	-0.993	-0.853	-0.831
α_{-6}	-1.054	-1.134	-0.974	-0.928
α_{-5}	-1.166	-1.284	-1.100	-1.030

α_{EYO}	MEMUNITS	MMSE	WAIS	ISLT
α_{-4}	-1.276	-1.445	-1.234	-1.134
α_{-3}	-1.388	-1.618	-1.382	-1.242
α_{-2}	-1.511	-1.806	-1.553	-1.351
α_{-1}	-1.653	-2.014	-1.754	-1.458
α_0	-1.817	-2.260	-1.987	-1.558
α_1	-1.990	-2.258	-2.238	-1.646
α_2	-2.161	-3.024	-2.520	-1.724
α_3	-2.336	-3.686	-2.841	-1.792
α_4	-2.536	-4.652	-3.158	-1.856
α_5	-2.750	-6.008	-3.506	-1.919
α_6	-2.950	-7.824	-3.648	-1.990
α_7	-3.123	-9.959	-4.035	-2.077
α_8	-3.272	-12.193	-4.645	-2.189
α_9	-3.436	-14.155	-5.065	-2.325
α_{10}	-3.650	-15.482	-5.314	-2.505
α_{11}	-3.850	-16.500	-5.501	-2.650
α_{12}	-4.050	-17.500	-5.700	-2.800
α_{13}	-4.250	-18.500	-5.900	-2.295
α_{14}	-4.450	-19.500	-6.100	-3.100
α_{15}	-4.650	-20.500	-6.300	-3.250

- **Frequency of cognitive assessments:** Every 12 months
- **Dropout:** 7% annual drop-out rate unrelated to outcome
- **Accrual:** The actual trial accrual is used. The 140 subjects are accrued over 975 days with the 35th, 70th, and 105th being enrolled on days 589, 758, and 918, respectively.
- **CDR-Global:** The trial has an inclusion criterion of a CDR-global of 1 or less. For each subject, a CDR-global is simulated based on their baseline cognitive composite. The simulated cognitive composite is calculated, and a subject is excluded (and replaced) if a CDR-global greater than 1 is simulated.

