2.2 Treatment Administration Schedule and Duration

Study Drug Solanezumab (LY2062430)

The proposed solanezumab treatment arm was initiated at 400 mg intravenously given every 4 weeks. Following the approval of Amendment 7 at their site, all subjects will sign the new ICF and initiate dose escalation per protocol starting at the 800 mg dose level for at least 2 doses and then to 1600 mg for the remainder of the study.

For the primary analysis, the treatment duration will last until the last subject enrolled has reached 48 months of treatment after initial randomization. Because of the length of trial enrollment, there will be subjects with greater than 48 months exposure with a maximum, estimated, duration near 78 months.

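### The TEAE table by TE ADA status uses ever-positive status with no time at risk; an onset-split, exposure-adjusted display should be added beside it

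*SAP*

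**What the plan says.** Four parts of the SAP fix this table.

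- **The table.** Appendix VIII, section 4.3.3 (Immunogenicity Statistical Analyses), gives the "number and percentage of solanezumab-treated patients experiencing TEAE (overall and by PT) by patient TE ADA status". The columns are TE ADA+, TE ADA- and TE ADA Inconclusive, and PTs are ordered by incidence in the TE ADA+ column.
- **The grouping.** Under the definitions in the same section, a subject who was ADA-negative at baseline is TE ADA+ with "at least one post-baseline status of ADA Present with titer" at or above twice the minimum required dilution. A subject positive at baseline needs a fourfold rise. The window is open-ended: "Post-baseline period observations for each subject includes all observations after the first administration of study drug".
- **The events.** Section 13.2: "TEAEs are defined as events that first occur or worsen (increase in severity) after the first dose of the study drug". ADA onset plays no part.
- **The follow-up.** Appendix VIII, section 2.2: "there will be subjects with greater than 48 months exposure with a maximum, estimated, duration near 78 months". The minimum for the last subject enrolled is 48 months, and those who withdraw have less.

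Section 4.3.3 also plans per-subject listings that set the ADA time course beside the adverse event, among them a listing of every TEAE in TE ADA+ subjects. It adds: "The time from first dose to the first TE ADA titer will be summarized cumulatively". Section 13.2 says of the overall TEAE summary: "The number of TEAEs per patient-year of exposure will also be presented". Neither measure is carried into the table by ADA status.

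**The concern.** The column a subject falls in depends on what happens over the whole of follow-up, and the events are counted over that same follow-up. Two things go wrong.

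First, a subject followed longer has more chance both to become TE ADA+ and to have any given TEAE. The TE ADA+ column can then show a higher percentage with no effect of antibodies at all.

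Second, events and time before the first TE ADA titre count as TE ADA+. If antibodies do raise the rate of some event, the antibody-free period dilutes the contrast.

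At stake is how a reader judges whether antibodies to solanezumab are linked to particular adverse events. This is the only tabulated comparison of TEAEs by ADA status in the section. Efficacy inference is not touched.

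**Working it through.** The SAP gives no figure for this bias, so there is nothing to reproduce. Its direction follows from the definitions. Its size needs assumptions.

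**Inputs from the SAP**
- Accrual (Appendix VI): 140 subjects over 975 days, with the 35th, 70th and 105th on days 589, 758 and 918. Analysis is when the last subject reaches 4 years, so the longest possible follow-up is 4 + 975/365.25 = 6.67 years, or 80 months, close to the 78 months stated.
- Drop-out (Appendix VI): "7% annual drop-out rate unrelated to outcome".
- Active arm (Appendix VIII, section 3.4): 52 mutation-positive subjects.

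**Assumed, not in the SAP**
- ADA onset at a constant hazard of 0.02 to 0.20 per year, or uniform over year 1 in 5% or 20% of subjects.
- First occurrence of one PT at 0.02, 0.05 or 0.20 per year.

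**Method.** Simulation of 2,000,000 subjects per setting. Tabulated ratio = (% with the event among ever-positive) / (% among never-positive). Split ratio = (events after onset / time after onset) / (events in ADA-free time / ADA-free time).

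**No true effect of ADA**

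| Setting | First events before onset, among TE ADA+ subjects with the event | Tabulated ratio |
|---|---|---|
| Constant hazard, 7% drop-out | 43% to 57% | 1.12 to 1.27 |
| Constant hazard, no drop-out | 43% to 57% | 1.01 to 1.03 |
| Onset in year 1, 7% drop-out | 12% to 17% | 1.03 to 1.04 |

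The split ratio is 0.98 to 1.01 in every setting.

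*One setting by hand.* Take ADA 0.10 per year, event 0.05 per year and 7% drop-out. Mean follow-up is 4.53 years in ever-positive and 3.79 years in never-positive subjects. Then 1 − exp(−0.05 × 4.53) = 20.3% and 1 − exp(−0.05 × 3.79) = 17.3%, a ratio of 1.17. The simulation gives 20.1% and 17.0%, a ratio of 1.18. The null distortion is thus almost entirely the difference in follow-up. Most of that difference comes from drop-out: the administrative spread alone gives only 1.01 to 1.03.

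**True threefold rise in rate after onset (7% drop-out)**
- At 0.05 events per year, the tabulated ratio is 2.01 to 2.37 with constant-hazard onset and 2.38 with onset in year 1.
- At 0.02 per year it is 2.2 to 2.65. At 0.20 per year it is 1.5 to 1.7.
- The split ratio is 2.97 to 3.02.

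Part of the shortfall is a property of percentages. Over a full 4 years at 0.05 per year, a threefold rate gives (1 − exp(−0.60)) / (1 − exp(−0.20)) = 0.451/0.181 = 2.49 even with no time before onset. Time before onset accounts for the rest, and rates per patient-year remove both.

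**Against sampling error.** In the hand-worked setting 32.4% become positive, so 0.324 × 52 ≈ 17 are TE ADA+ and 35 are not. The standard error of the difference is √(0.201 × 0.799/17 + 0.170 × 0.830/35) = 11.6 percentage points, against a bias of 3.1. In the worst null setting (58.1% against 47.5%, about 28 and 24 subjects) the bias is 10.6 points and the standard error is √(0.581 × 0.419/28 + 0.475 × 0.525/24) = 13.8 points.

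**The case against.** A reader might infer that this is the one table meant to show antibody-related harm, so that the SAP's safety conclusion on ADA rests on it. The text does not support that. Section 4.3.3 gives the table no purpose of its own. The sentence about clinical relevance comes afterwards and introduces the evaluation of specific acute and non-acute events and the timed listings. The table is descriptive, with no test, interval or decision rule.

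The listings answer much of the timing concern. They cover every TEAE of every TE ADA+ subject against the ADA time course. If 10% to 20% of 52 subjects became positive, that is about 5 to 10 people, and each event before onset could be seen. What they cannot give is a denominator, or the same information for never-positive subjects. No rate comparison can be built from them.

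Splitting at onset has weaknesses too. Onset is known only to the nearest sample. Section 4.3.3 says circulating drug can interfere with ADA detection, so time before the first titre is not proven antibody-free. TE ADA Inconclusive is defined over a subject's whole set of post-baseline samples and cannot be split by time. These points stand, and they are why the new display should supplement the table rather than replace it.

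**Conclusion.** The point holds as a minor gap in a descriptive safety summary. The table groups by ever-positive status, counts events before the first TE ADA titre in the TE ADA+ column, and takes no account of time at risk.

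With no true effect the distortion is modest: 1.01 to 1.04 when onset is in year 1 or there is no drop-out, and 1.12 to 1.27 with constant-hazard onset and 7% annual drop-out. A threefold rise in rate is diluted to about 2.0 to 2.4 at 0.05 events per year. All of these rest on assumed ADA and event rates and on drop-out unrelated to outcome. In a cohort of about 52, chance will often exceed the bias. The documents do not support saying that the ADA safety assessment as a whole is distorted.

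**What to change.** Keep the existing table. In Appendix VIII, section 4.3.3, add a companion display for solanezumab-treated subjects, overall and by PT:

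1. Number and percentage of TE ADA+ subjects with a TEAE starting on or after the date of the first sample with a TE ADA titre.
2. TEAEs per patient-year in two states: TE ADA+ time, from that date onward; and ADA-negative time, meaning all time in TE ADA- subjects plus the time of TE ADA+ subjects before that date. Each event goes to the state in force at its onset.
3. TE ADA Inconclusive subjects in a separate column, outside both states.
4. A footnote that onset is known only to the nearest sample and that drug interference can delay detection, so events shortly before the first positive sample may be misclassified.

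The cost is a few lines of SAP text and one more table. The date is already needed for the time-to-first-titre summary, and the rate per patient-year is already planned in section 13.2. No new data are required. The downside is the possible misclassification in item 4, which could move antibody-related events into ADA-negative time. That is a reason to show both displays together.
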